8.1.2 Analysis of the secondary judgement criteria

The identification of predictive factors of pre-hospital ECMO success will be done first by a univariate analysis using a chi-squared test (or a Fisher's exact test if the test application conditions are not verified) for the qualitative variables, and with a Student's test (or Wilcoxon if the test application conditions are not verified) for the quantitative variables.

Next, a multivariate analysis by logistic regression will enable the simultaneous study of factors associated with the pre-hospital success of ECPR by adjustment to the different potentially confounding variables. In the multivariate model only variables that are significant in univariate at the threshold $p=0.20$ will be used. The model variables will be selected by a backward stepwise method and tested by the likelihood ratio test. The association between the success of pre-hospital ECPR and the associated factors will be expressed in odds ratio (OR) and estimated with its confidence interval at 95%.

The tests will be bilateral and a level of significance $p<0.05$ will be considered as significant.

9 RESEARCH OUTLINE AND PROCEDURE

9.1 Recruitment method

This is a pragmatic study aimed at including all consecutive eligible patients. The investigators will seek the participation of all the victims of out-of-hospital cardiac arrest who are cared for and who present the required criteria (eligibility and non-eligibility). A record of potentially eligible patients will be kept updated in each participating site.

In practice, patients are included and randomised on the spot where the cardiac arrest occurs. The inclusion criteria are verified by the physician responsible for implementing ECPR on the spot.

9.2 Feasibility

At Necker, 40 patients per year benefit from ECPR for refractory cardiac arrest. The other investigator sites should quickly reach this rate of inclusion. It is reasonable to estimate a research period of 4 years.

9.3 Research procedure for each patient

Baseline visit: Patient recruitment and inclusion phase

When a victim of cardiac arrest with "no flow" for less than 5 minutes is taken under care in an out-of-hospital setting, a mobile ECMO team is rushed to the spot at the 10th minute. This team verifies the inclusion criteria. The patient is included and randomised when all the eligibility criteria are met as of the 20th minute of cardiac arrest. Randomisation is done by drawing of lots from an envelope. In the pre-hospital ECMO group, treatment starts immediately. In the in-hospital ECMO group, medicalised resuscitation is continued and the patient is transferred to the hospital for the implementation of circulatory support. The ECPR success rate and implementation time are noted and compared. The family is informed at inclusion or at intensive care arrival. The patient is informed as soon as possible, if he/she is alive.

Follow-up visit on discharge from intensive care , at day 28, at 2, 6 and 12 months::

These visits should enable the evaluation of the patient outcome: survival, brain death or demise. A neurological exam evaluates the CPC score. The numbers of packed red blood cell transfusions in the first 24 hours and cases of sepsis over the course of hospitalisation are noted.

At 12 months, the physician will contact the patient to evaluate the patient outcome.

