When a victim of cardiac arrest with strict "no flow" for less than 5 minutes is taken under care in an out-of hospital setting, a mobile ECPR team is rushed to the spot at the 10th minute of cardiac arrest. The 2 physicians in this team verify the inclusion criteria. The patient is included when all the eligibility criteria are present, between the 20th minute and the 40th minutes of cardiac arrest. Treatment starts immediately after randomisation. The success rate and ECMO implementation time are noted and compared. The family is informed at inclusion or at intensive care arrival. The patient is informed as soon as possible, if he/she is alive.

Follow-up visit on discharge from intensive care, at day 28, at 2, 6 and 12 months.: These visits should evaluate the patient outcome. The CPC score and the number of transfusions and infections during hospitalisation are evaluated.

Duration of the study: 4 years

Participation period for one patient: 1 Year

Number of investigator sites: 4

Expected results: An increase of 5% to 20% of survival for victims of out-of-hospital refractory cardiac arrest, with a good neurological prognosis.

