5 POPULATION ELIGIBILITY CRITERIA

5.1 Inclusion criteria for ill subjects

Eligible patients have the following combination of criteria:

- Adults over 18 years of age and under 65 years of age
- And Refractory cardiac arrest (defined by the failure of professionals to resuscitate at the 20th minute of cardiac arrest with a minimum of 3 AED or equivalent analyse)
- And Beginning of external cardiac massage within the first 5 minutes after cardiac arrest (no flow < 5 min.) with persistent shockable rhythm **or** persistent signs of life during resuscitation: spontaneous movement, absence of mydriasis and/or pupillary response, spontaneous breathing movements
- And Medical cause of the cardiac arrest
- And ETCO₂ above 10 mm Hg at the time of inclusion
- And Absence of major co-morbidity.
- And ECPR team available and on-site before the 40th minute

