6 EXPERIMENTAL DESIGN

This is a multi-centre prospective superiority randomised study. The results are compared to the percentage of success of in-hospital use of ECMO. Due to the type of technology used, it is impossible to implement a blind.

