10.2.2 Data entry

Data entry will be carried out on electronic media via a web browser.

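### Arms are assigned by drawing lots from an envelope at the scene of an open-label trial, where the ECPR physician also judges eligibility and no concealment step is described

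*Combined protocol and SAP*

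**What the plan says.** - **Method.** Section 9.3: "Randomisation is done by drawing of lots from an envelope". Nothing more is said about how the sequence is made, held or revealed.
- **Place.** Section 9.1: "In practice, patients are included and randomised on the spot where the cardiac arrest occurs".
- **Who judges eligibility.** Section 9.1: "The inclusion criteria are verified by the physician responsible for implementing ECPR on the spot". The protocol summary gives the task to the mobile ECPR team: "The 2 physicians in this team verify the inclusion criteria".
- **Blinding.** Section 6: "Due to the type of technology used, it is impossible to implement a blind".
- **Criteria.** Section 5.1 mixes measured items (age, ETCO₂, no-flow time, number of rhythm analyses) with items that need judgement. Examples are signs of life and "And Absence of major co-morbidity", which has no list or threshold. The summary allows inclusion at any time from the 20th to the 40th minute.
- **Related safeguards.** Section 9.1 aims to include all consecutive eligible patients and adds: "A record of potentially eligible patients will be kept updated in each participating site".
- **Infrastructure.** Section 10.2.2: "Data entry will be carried out on electronic media via a web browser".

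Sections 6 to 9.3 do not mention sealing, opacity, numbering, a sequence holder, registration before the draw, an opening log, blocking or stratification. Section 8 names no analysis population, so it does not say that a patient dropped after the draw is still counted.

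**The concern.** In an unblinded trial, concealing the next assignment until the patient is irrevocably entered is the main protection against selection bias at entry. Drawing a lot is physically repeatable in a way that opening the next numbered, sealed envelope is not. Without registration before the draw, a patient can also be reclassified as ineligible after the arm is seen, and the judgement-based criteria make that easy to justify.

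The protocol expects 20% success in one arm and less than 5% in the other, so a clinician who shares that expectation has a natural pull towards pre-hospital ECPR for a promising patient. Even under the planned effect only about 26 successes are expected (105 × 0.20 + 105 × 0.05 = 26.25), so a modest shift in case mix can matter. Later analysis cannot reliably repair it.

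**Working it through.** **1. The plan's own figure.** Inputs from section 7: 5% versus 20%, alpha 5%, power 90%, 105 per group. Two-sided testing is taken from section 8.1.2. With pooled rate 0.125 and difference 0.15:

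- n = [1.96·√(2·0.125·0.875) + 1.2816·√(0.05·0.95 + 0.20·0.80)]² / 0.15² = (0.9167 + 0.5838)² / 0.0225, which rounds up to 101 per group.
- Allowing for the 5% loss in section 9.6: 101 / 0.95, rounded up, is 107.
- Power at 105 per group: Φ[(0.15·√105 − 0.9167) / 0.4555] = Φ(1.362) = 91.3%.

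The stated 90% power is therefore supported at 105 per group. The allocation point does not depend on it.

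**2. What steering could do.** No figure in the documents measures this, so what follows is an illustration. Assumptions:

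- no true treatment effect;
- half the patients have a visibly better prognosis, with success rate g, and the other half have rate b;
- in a fraction f of allocations the better-prognosis patient goes to pre-hospital ECPR and the poorer-prognosis patient to in-hospital ECPR, and the rest are random;
- 105 per arm, uncorrected two-sided chi-squared test at 5%.

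Then, with m = (g + b)/2:

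- pre-hospital rate = (1 − f)·m + f·g
- in-hospital rate = (1 − f)·m + f·b
- spurious difference = f·(g − b)

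Example with g = 8%, b = 2%, f = 0.20: 0.8 × 5% + 0.2 × 8% = 5.6%, against 0.8 × 5% + 0.2 × 2% = 4.4%, a spurious 1.2 points.

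Exact two-sided false-positive rates, summing binomial probabilities over all outcomes:

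| Better / poorer half | No steering | 10% | 20% | 30% |
|---|---|---|---|---|
| 8% / 2% (overall 5%) | 4.4% | 4.9% | 6.1% | 8.2% |
| 9% / 1% (overall 5%) | 4.4% | 5.2% | 7.4% | 11.3% |
| 10% / 0% (overall 5%) | 4.4% | 5.6% | 9.1% | 15.4% |
| 16% / 4% (overall 10%) | 5.2% | 6.2% | 9.2% | 14.3% |

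Simulation with arm sizes left to chance (40,000 trials of 210 patients) gives slightly higher values for the 5% scenarios: up to about 10% at 20% steering and about 16% at 30%. The combined ranges are about 6–10% and 8–16%.

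**3. Direction.** Most of these false positives favour pre-hospital ECPR. In the 8%/2% row they are 5.3 of the 6.1 points at 20% steering and 7.7 of the 8.2 at 30%. In the 10%/0% row they are 15.3 of the 15.4 at 30%.

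**4. How many patients that means.** Steering 20% of 210 is 42 allocations. About half would have gone to that arm anyway, so about 21 patients change arm. Steering 5 or 10 allocations in the 16%/4% scenario gives 5.3% and 5.5%, against 5.2% with none.

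**5. Site balance.** With simple randomisation and about 52 patients at each of 4 sites (equal sites assumed; 210/4 = 52.5), the arms at a given site differ by 10 or more with probability about 21%. An overall split of 95/115 still gives 90.9% power.

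**The case against.** The fair reply is that a one-sentence description is not evidence of a bad procedure. Sealed, numbered envelopes are compatible with that sentence. Section 9.3 also orders the steps (criteria met, then inclusion and randomisation). Several criteria are measured, consecutive inclusion is intended, and each site keeps a record of potentially eligible patients. All of this stands. It limits the point to what is not described, and it makes the record a partial safeguard. The record is not tied to the draw, however, and it does not fix any patient before the arm is known.

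A reader might infer four stronger things that the documents do not support:

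- **That allocation is unconcealed.** The protocol is silent and does not say that concealment is absent.
- **That the ECPR physician draws the lot.** Section 9.3 does not say who draws. The ECPR team is the only trial team placed at the scene, so it presumably does, but the summary puts two physicians in that team and a division of roles is possible.
- **That moving a handful of patients is enough to produce a positive result.** Step 4 contradicts this. A few moved patients could tip a borderline result, but they leave the overall error rate near 5%.
- **That lack of site stratification lets the arms be steered.** Simple randomisation is valid, and stratification does not prevent steering.

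**Conclusion.** The point holds as a weakness in the described method that should be corrected. Lots are drawn at the scene of an unblinded trial, eligibility is judged by the physician who delivers the experimental strategy, and no concealment step is described. It is a risk and not evidence that any allocation was steered.

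On the assumptions above, sustained steering of 20% of allocations would raise the two-sided false-positive rate from about 5% to about 6–10%, and 30% to about 8–16%, mostly in favour of pre-hospital ECPR. At 10% the rise is small. The prognosis split, the overall success rates and the steering fractions are all assumed. The direction follows if better-prognosis patients are steered towards pre-hospital ECPR. Site balance is a secondary matter and not part of the defect.

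**What to change.** Replace the allocation sentence in section 9.3 with wording such as:

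> Allocation is central, through the web data-entry system or a telephone link to it. The patient and the time are registered before the arm is shown, and every registered patient is analysed in the allocated arm.

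If connectivity at the scene is a concern, use sequentially numbered, opaque, sealed envelopes for each site, prepared centrally. Mark each with a patient identifier and the time before opening, and reconcile them against the record in section 9.1. In either case, state who generates and holds the sequence and who performs the allocation at the scene.

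Stratifying by site with undisclosed, varying block sizes is an optional addition.

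**Cost.** The electronic route needs a randomisation module added to the existing web system and a few seconds at the scene. The other route needs one set of prepared envelopes per site and adds essentially no delay. The sample size does not change: 105 per group still gives 91.3% power.

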9.4 Scheduled participation period for each patient

The participation period is a maximum of 1 year.

9.5 Scheduled duration of the research

The recruitment period will last 36 months. The monitoring period up to the end of the study will last for 1 year for each patient included in the study. The total duration of the study will therefore be 4 years.

9.6 Methods for monitoring excluded patients

All withdrawals from the study should be documented and the investigator should specify the reason.

For patients considered to be lost to follow-up, the case report form should be filled out up to the last visit. The investigator will try his/her utmost to contact the patient, find out the reason for withdrawal from the trial and his/her health status. Patients who withdraw will not be re-included in the study. Their treatment number will not be reused. These patients will nevertheless, be monitored in a service not included in the protocol.

Lost to follow-up: we will consider a maximum of 5% of the patients in the entire cohort to be lost to follow-up.

10 DATA MANAGEMENT

10.1 Right to access source data and documents

10.1.1 Access to data

In accordance with GCPs:

- the sponsor is responsible for obtaining the permission of all parties involved in the research to guarantee direct access to all locations where the research will be carried out, to the source data, to the source documents and the reports, with the goal of quality control and audit by the sponsor
- the investigators will make available to those in charge of monitoring, quality control and audit relating to the research the documents and personal data strictly necessary for these controls, in accordance with the legislative and regulatory provisions in force.

10.1.2 Source documents

Source documents are defined as any original document or object that can prove the existence or accuracy of a piece of information or a fact recorded during the research. These documents will be kept for 15 years by the investigator or by the hospital in the case of a hospital medical file.

10.1.3 Data confidentiality

Those responsible for research quality control will take all necessary precautions to ensure the confidentiality of information about the research, the research subjects and in particular the identity of the subjects and the results obtained.

These individuals, as well as the investigators themselves, are subject to professional secrecy (in accordance with the conditions set out in Articles 226-13 and 226-14 of the Penal Code).

During or after the research, the data collected about the research subjects and sent to the sponsor by the investigators (or any other specialised parties) will be made non-identifying.

Under no circumstances should the names and addresses of the subjects involved be shown.

The sponsor will ensure that each research subject has given permission in writing for access to personal information about him or her which is strictly necessary for the quality control of the research.

10.2 Data processing and storage of documents and data

10.2.1 Identification of the manager and the location(s) for data processing

The data management and the statistical analysis will be done by INSERM U970.

10.2.2 Data entry

Data entry will be carried out on electronic media via a web browser.

10.2.3 Data processing (CNIL, the French Data Protection Authority) in France

The computer file used for this research is implemented in accordance with French (amended “Informatique et Libertés” law governing data protection) and European (General Data Protection Regulation – GDPR) regulations.

The processing of personal data for this research falls under the scope of the provisions of Articles 53 to 61 of the Law of 6 January 1978 relating to information technology, data files and privacy, modified by Law No. 0204-801 of 6 August 2004.

10.2.4 Archival

Specific documents for research relating to a medication for human use will be archived by the investigator and the sponsor for a period of 15 years after the end of the research.

10.3 Ownership of the data

AP-HP is the owner of the data, which cannot be used or disclosed to a third party without its prior approval.

11 ETHICAL AND LEGAL CONSIDERATIONS

The research will be supervised in line with the sponsor's standard operating procedures. The progress of research in investigational centres and the treatment of subjects will be conducted in line with the Declaration of Helsinki and current Good Clinical Practice.

11.1 Conditions for information of subjects

The ECPR Team will inform the family's subject in emergency at inclusion or at intensive care admission. If the patient is conscious at any time, he/she will be informed by the doctor in charge.

The information given by the subject will be noted in their medical records. The absence of opposition to the participation of the subject will be notified in his medical records by the investigator who collects it.

11.2 Request for an opinion from the Comité de Protection des Personnes (CPP, ethical review board)

The principal investigator obtains for this research prior to starting the research, the favourable opinion of the appropriate CPP (Ile de France II), within the scope of its authority and in accordance with the legislative and regulatory provisions in force.

11.3 Request for the opinion of the CCTIRS (advisory committee on the processing of research information in the area of health) and request for authorisation from CNIL (French data protection authorities)

As the processing of personal data for this research does not fall under the scope of the MR 001 méthodologie de reference, the sponsor must obtain the opinion of the CCTIRS and the authorisation of the CNIL.

11.4 Modifications to the research

Any substantial modification to the protocol by the coordinating investigator must be sent to the sponsor for approval. After approval is given, the sponsor must obtain, prior to starting the research, a favourable opinion from the CPP within the scope of their respective authorities.

The information sheet can be revised if necessary, in particular if there is a substantial modification to the research.

STUDY OUTLINE FOR EACH PATIENT SELECTED

Period	Selection		
Visit	Out-of-hospital	Admission to the ICU	Discharge from the ICU
Month	D0	D0	Dn
Inclusion - non-inclusion criteria, Information	X	X	
Information	X	X	
Inclusion	X		
Treatment: ECPR implementation	X		
Clinical exam	X		X
Neurological exam	X		X
